10.6. Appendix 9: Definitions

10.6.1. General

TERM	hVIVO Services Limited Definition
Completion (of a participant's participation in the study)	A participant will be considered to have completed the study after his/her attendance at the last planned study visit, or the last unscheduled visit as applicable.
Baseline	For safety assessments the nearest assessments completed prior to vaccination will be used as the baseline measure, unless stated otherwise.
Enrolment (of a participant into the study)	A participant will be considered to be 'enrolled' into the study once he/she has been randomised, dosed, or inoculated (whichever occurs first).
Infectious titre	The titre of virus inoculum producing viral infection in a participant. The term 'titre' applies to the quantity or concentration of virus inoculum (depending on the units documented).
Quarantine group	A group of participants who are admitted to and are resident in the Quarantine Unit for a particular quarantine period (i.e., participants whose Day 0 and scheduled discharge date are the same).
Quarantine period	The period of time when clinical trial participants are isolated in the Quarantine Unit during a HVC study.
Randomisation number	The number allocated to a participant at randomisation.
Participant number	The unique number assigned to a participant on the hVIVO participant database, which is used to identify the participant prior to randomisation.
Viral Challenge (or Challenge)	The inoculation of a participant with virus inoculum. By definition, the day of Viral Challenge is Day 0.

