
 To evaluate the safety and reactogenicity of RSVpreF, when compared to placebo 	
To evaluate the incidence of the following endpoints:
 
 Occurrence of solicited local reactions and systemic events within 7 days (i.e., on the day of vaccination and 6 subsequent days) after vaccination. Occurrence of unsolicited adverse events (AEs) within 30 days (i.e., on the day of vaccination and 29 subsequent days) after vaccination Occurrence of medically attended AEs (MAEs) and serious adverse events (SAEs) from vaccination (Day -28) up to study end (Day +155).

 To evaluate the safety of the RSV challenge model. 	
To list the incidence of the following endpoints:
 
 Occurrence of unsolicited AEs within 30 days post-viral challenge (Day 0) up to Day +28 follow up. Occurrence of SAEs related to the viral challenge from the viral challenge (Day 0) up to Day +28 follow up. Occurrence of haematological and biochemical laboratory abnormalities during the quarantine period. Use of concomitant medications within 30 days post-viral challenge (Day 0 up to Day +28 follow up).
TERTIARY	
Tertiary/exploratory endpoints include but are not limited to the following.	

 To evaluate the effect of baseline immune status on immunogenicity and efficacy of the RSVpreF, when compared to placebo 	
 The primary, secondary, and tertiary endpoints may be explored in relation to the baseline status of participants and the response to vaccination.

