4.1. Overall Design

This is a randomised, Phase 2a, double blind, placebo-controlled study to evaluate the safety, immunogenicity and efficacy of an RSV vaccine against RSV-A Memphis 37b infection in healthy participants.

The total duration of study participation for a participant is approximately 6 months after vaccination, with the following sequence and duration of study periods:

Screening Phase:

- Screening prior to vaccination from Day -84 to Day -29 (Day -118 for RSV serology) Pre-screening data collected through the hVIVO generic screening process prior to signing the study specific consent form, and prior to vaccination from Day -84 to Day -29 (Day -118 for RSV serology) may be transferred to this study after study-specific consent form has been signed by the participant. Pre-screening data obtained prior to this window can be re-assessed any time prior to vaccination from Day -84 to Day -29.

Vaccination Phase:

- Vaccination on Day -28 (± 3 days), participants will be randomised 1:1 to receive RSVpreF or placebo
- Follow up clinic visit 1 day post vaccination
- Follow up clinic visit 7 days post vaccination (± 1 day)

Quarantine Phase:

- Admission to the Quarantine Unit on Day -2/-1; resident in the Quarantine Unit for approximately 15 days, from admission on Day -2 to planned discharge on Day +12.
- Challenge with Challenge Virus on Day 0.
- Discharge from quarantine planned on Day +12

Follow-Up Phase:

- Day +28 (± 3 days).
- Day +155 (± 14 days)

Participants will be pre-screened for susceptibility to RSV infection, i.e., have levels of RSV neutralising antibodies compatible with susceptibility to RSV infection.

Participants will be randomised to receive a single intramuscular dose of RSVpreF or Placebo on Day -28 (± 3 days):

- **Reference article product**
 - PF-06928316 also known as RSVpreF
 - Dose: 120mcg

- **Placebo product**

- Placebo to match vaccine

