4	
A severe non-serious adverse reaction (i.e. severe non-serious adverse events considered at least possibly related to the IMP administration) is reported in two participants, independent of whether or not within the same system-organ/class.
	
If such a status occurs at any point during the study, then further administration of RSVpref will not take place. The PI and the SMM will review the data and make decisions on whether it is appropriate to recommence dosing (via a substantial amendment, if indicated) or terminate the study.
 
Regulatory authority approval via a substantial amendment would be required in order to recommence the study.

In any event, participant follow-up should continue until resolution or stabilisation of AEs and final follow-up on Day +155 (\pm 14 days).

8. Study Assessments and Procedures

Unless otherwise stated, study assessments will be performed according to hVIVO SOPs.

Study procedures and their timing are summarised in the SoA. Protocol waivers or exemptions are not allowed. Adherence to the study design requirements, including those specified in the SoA, is essential and required for study conduct. Immediate safety concerns should be discussed with the Sponsor upon occurrence or awareness to determine if the participant should continue or discontinue study intervention

All screening evaluations must be completed and reviewed to confirm that potential participants meet all eligibility criteria. The investigator will maintain a screening log to record details of all participants screened and to document eligibility or record the reasons for screening failure, as applicable.

For all study assessments, the value obtained nearest to dosing will be used as the baseline measure for assessments, unless stated otherwise.

Procedures conducted as part of the hVIVO Generic Screening process and obtained before signing of the study specific Informed Consent Form (ICF) may be utilised for screening or baseline purposes provided the procedures met the protocol-specified criteria and were performed within the time frame defined in the SoA.

Where applicable, unless otherwise stated, normal ranges will be identified in the Investigator Trial Master File (TMF).

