A 15% drop in a spirometry value (compared to baseline) confirmed by a repeat on the same day, will be a Grade 1 (mild) AE. The PI/Investigator will use his/her clinical judgement to assign severity grades above Grade 1, based on evaluation of clinical signs and symptoms. If the repeated value has returned to normal an AE will not be raised.

Laboratory Values

Deterioration in a laboratory value (compared to baseline) should only be reported as an AE if the deterioration fulfils the criteria for an AE. If deterioration in a laboratory result is associated with clinical signs and symptoms, the sign or symptom will be reported as an AE and the associated laboratory result will be considered as additional information.

The Investigator and/or SMM will judge whether abnormal laboratory values are clinically significant or not clinically significant, and record this in the source document. This entry should be signed and dated by the relevant Investigator. Laboratory abnormalities detected at screening will be considered as part of the medical history and will not be reported as AEs

Challenge Virus associated laboratory abnormalities (e.g.: elevated ALT, AST or GGT; decreased neutrophils) may be recorded as AEs (at the discretion of the Investigator).

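### The default safety baseline is a pre-vaccination value; no pre-challenge baseline is defined for changes after RSV challenge, although admission values are collected

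*Combined protocol and SAP*

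**What the plan says.** Section 3 has two secondary safety objectives. One concerns the vaccine against placebo, the other the challenge model. The second includes "Occurrence of haematological and biochemical laboratory abnormalities during the quarantine period".

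Two general baseline rules appear. Section 10.6.1: "For safety assessments the nearest assessments completed prior to vaccination will be used as the baseline measure, unless stated otherwise". The opening of Section 8: "For all study assessments, the value obtained nearest to dosing will be used as the baseline measure for assessments, unless stated otherwise". Section 8 also lets results from the generic screening process stand in; they "may be utilised for screening or baseline purposes" if they meet the protocol criteria and fall within the scheduled window.

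Several adverse event rules refer to baseline. The only numeric one is in Section 10.3.6.2: "A 15% drop in a spirometry value (compared to baseline) confirmed by a repeat on the same day" is a Grade 1 event. Laboratory values and vital signs (Sections 8.7 and 10.3.6.2) and ECG (Section 8.9) are also compared with baseline, with judgement of clinical significance on top.

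Section 9.5 leaves the description of all baselines to the SAP. No SAP text is among the documents reviewed.

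**The concern.** The two safety objectives concern two exposures about four weeks apart, and each needs the state just before its own exposure as reference. A pre-vaccination value suits the vaccine objective. For the challenge it is an older reference than the data require, because most of the relevant tests are repeated on entry to quarantine.

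Two things are at stake. First, a change-from-baseline summary for the challenge period also contains whatever happened between screening or vaccination and admission. Second, where baseline decides whether an adverse event is recorded, drift before challenge moves the threshold. A fall during quarantine may be recorded too readily in one participant and missed in another. The tests with the oldest baseline include ECG and cardiac enzymes, which the risk table in Section 2.2.1 relies on to monitor for myocarditis after challenge.

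**Working it through.** No power or sample size figure is involved. The check is day arithmetic, a reading of the schedule, and one illustration.

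**1. Day anchors.** Section 10.6.1: "By definition, the day of Viral Challenge is Day 0". Section 4.1: "Screening prior to vaccination from Day -84 to Day -29 (Day -118 for RSV serology"). Vaccination is on Day -28, plus or minus 3 days. Admission tests are on Day -2 or Day -1.

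**2. Which value is the baseline?** Nine safety assessments in the Schedule of Activities (Section 1.3) are repeated in quarantine.

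| Assessment | Last scheduled value before vaccination | Admission value |
|---|---|---|
| Haematology, cardiac enzymes, 12-lead ECG, spirometry | Screening | Yes |
| Biochemistry | Vaccination day if the optional sample is taken, otherwise screening | Yes |
| Vital signs, temperature, urinalysis, complete physical examination | Vaccination day | Yes |

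So 4 of 9 have only a screening value. This becomes 5 of 9 when the optional biochemistry is not taken. The other 4 have a vaccination-day value.

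**3. Age of the baseline** (challenge day or test day minus baseline day).

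| Baseline | Days before challenge | Days before a Day 11 test |
|---|---|---|
| Screening | 0 - (-29) = 29 to 0 - (-84) = 84 | 11 + 29 = 40 to 11 + 84 = 95 |
| Vaccination day | 28 - 3 = 25 to 28 + 3 = 31 | 11 + 25 = 36 to 11 + 31 = 42 |
| Admission | 1 to 2 | 12 to 13 |

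Day 11 is used because Section 2.2.1 places ECG and cardiac enzymes on Days 4, 7 and 11. A footnote to the schedule could be read as allowing 84 days before vaccination instead of before challenge. The maximum age at challenge would then be 84 + 25 = 109 to 84 + 31 = 115 days. The figure of 84 follows the protocol's own day numbering.

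**4. Effect on the spirometry rule.** Let s be the relative shift in FEV1 from screening to admission. The threshold is 0.85 times the screening value, so the fall from the admission value needed to reach it is 1 - 0.85/(1 + s). The documents give no value for s; the shifts below are assumptions. With a screening FEV1 of 4.00 L (also assumed; it cancels), the threshold is 0.85 x 4.00 = 3.40 L.

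| Assumed shift s | Admission FEV1 | Fall during quarantine that reaches the threshold |
|---|---|---|
| -10% | 3.60 L | 1 - 3.40/3.60 = 5.6% |
| -5% | 3.80 L | 1 - 3.40/3.80 = 10.5% |
| 0 | 4.00 L | 15.0% |
| +5% | 4.20 L | 1 - 3.40/4.20 = 19.0% |
| +10% | 4.40 L | 1 - 3.40/4.40 = 22.7% |

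**5. The two baseline rules side by side.** Section 10.6.1 ties the baseline to a value before vaccination. Section 8 ties it to the value nearest to dosing, without saying before. Section 6.4 describes dosed participants as receiving both the study intervention and the challenge virus, so dosing in Section 8 could mean either event. Neither rule names a pre-challenge baseline.

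**The case against.** The strongest reply is that these are defaults. Both rules yield to exceptions stated elsewhere, and Section 9.5 hands baselines to the SAP. This stands in part: the protocol does not show which baseline the final tables will use. It does not settle the matter for adverse events. Those are judged while participants are in quarantine, whereas Section 9.4.1 requires the final SAP to be signed only before the Day 28 analysis. The spirometry rule also needs a same-day repeat. If the reference in use means that the threshold is not crossed, that repeat may not be done, and a later SAP cannot supply it.

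Second, the challenge-safety endpoints in Section 3 are listed incidences, and laboratory abnormalities are not defined as changes from baseline. This stands. Counts against normal ranges do not depend on the baseline.

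Third, other safeguards already separate earlier findings. Section 10.3.1 excludes conditions present before challenge that do not worsen. Sections 10.3.6.1 and 10.3.6.5 record onset and weigh the challenge virus as a cause apart from the vaccine. Laboratory, vital-sign and ECG changes also need clinical judgement. This narrows the exposure to changes at admission too small to count as findings themselves, chiefly under the numeric spirometry rule.

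Fourth, the placebo arm is challenged without vaccine, and Section 9.6.8 presents safety data by arm. Vaccine effects can therefore enter only the RSVpreF arm. Drift over time can enter both.

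**Conclusion.** The point holds as a cheap improvement to a descriptive secondary safety analysis. It does not touch the primary efficacy analysis. As written, the default reference for challenge-period changes is 29 to 84 days old at challenge for four assessments (five without the optional biochemistry) and 25 to 31 days old for the other four, when one 1 to 2 days old is available.

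Three stronger readings are tempting, and the documents do not support them:

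- A reader might infer that every change in quarantine is measured from a screening value up to 84 days old. Four of the nine assessments have a vaccination-day value, and 84 days is the maximum of a range.
- A reader might infer that challenge safety cannot be read separately from vaccine safety. The endpoints are listed incidences, the placebo arm is unvaccinated, and onset and cause are recorded.
- A reader might infer that the final analysis will use this baseline. The SAP may override it.

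The conclusion rests on the schedule as read above and on the protocol's day numbering. The FEV1 figures illustrate direction and scale under assumed shifts of 5% to 10% either way; they do not estimate how often misclassification would occur.

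**What to change.** 1. Reconcile Section 8 with Section 10.6.1, and state which event dosing refers to.
2. Keep the last value before vaccination as the baseline for vaccine safety.
3. Define the last value before inoculation (Day -2, Day -1 or Day 0 pre-challenge) as the baseline for laboratory, ECG, vital-sign and spirometry changes from challenge onward, and apply it to the baseline comparisons in Section 10.3.6.2. The 15% criterion itself is not in question here.
4. Carry both definitions into the SAP, and report the change from the pre-vaccination value to admission separately as the vaccination-period change.

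All the values are already scheduled, so no visit or sample is added. The cost is protocol and SAP wording and one extra set of change-from-baseline tables.

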10.6.2. Study definition of infection and illness

TERM	CRITERIA
Seroconversion	Not applicable for RSV.

TERM	CRITERIA
Lower Respiratory Tract Illness (LRTI)	
Any one of the following signs and/or symptoms on two consecutive scheduled assessments, at least one of which must feature Grade 2 severity, or if any of the following attain Grade 3 severity once:
 
 ○ Self-reported symptoms: cough, shortness of breath, chest tightness and wheeze ○ Physician findings: Abnormal breath sounds externally (e.g. stridor, wheezing) and on chest auscultation (rhonchi, crepitations or other).
Upper Respiratory Tract Illness (URTI)	
Any one of the following signs and/or symptoms on two consecutive scheduled assessments, at least one of which must feature Grade 2 severity, or if any of the following attain Grade 3 severity once:
 
Self-reported symptoms: rhinorrhoea (runny nose), nasal congestion (stuffy nose), sore throat, sneezing.
 
Physician findings: nasal discharge, otitis, pharyngitis, sinus tenderness.

Systemic Illness	
Fulfils the criteria for febrile illness, or fulfils the definition of upper respiratory tract illness and/or lower respiratory tract illness
 
And
 
Any one of the following symptoms on two consecutive scheduled assessments, at least one of which must feature Grade 2 severity, or if any of the following attain Grade 3 severity once
 
 • malaise • headache • muscles and/or joint ache • chilliness • feverishness
Febrile Illness	Any occurrence of temperature $\geq 37.9^{\circ}\text{C}$
Viral shedding	
One or both of the following definitions must be met (between Day +2 and discharge from quarantine):
 
 • At least 2 positive quantifiable detections by viral load qPCR assay specific for the challenge virus, reported on 2 or more consecutive days and from 2 independent samples (which can either be the same type of sample or different e.g. throat swab and nasal wash or 2 nasal wash samples); • One positive detection by viral load qPCR assay, specific for the challenge virus, in which an aliquot of the same sample has also tested positive in a viral culture assay appropriate for detecting the challenge virus.

TERM	CRITERIA
Laboratory confirmed RSV infection	Viral shedding definition has been met.

11. References

